4.4.2 Screening exclusion criteria

Patients meeting any of the following criteria will not be included in the study:

1. Any patient who develops signs and symptoms of LRTD after being hospitalized for ≥ 48 hours (either at current hospital, another transferring hospital, or a combination of these), unless admitted with current, previous proven, or suspected COVID-19 infection.
2. Previously enrolled participants readmitted ≤ 7 days after discharge for their study qualifying admission, unless admitted with current, previous proven, or suspected COVID-19 infection
3. At the time of enrolment, an LRTD-related diagnosis has been excluded or another diagnosis confirmed (for example, patient was found to have fever and tachypnoea due to an intraabdominal process such as cholecystitis)

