5.1 Patients missed by consent

This study seeks to describe and ascertain the disease burden and outcomes attributable to acute LRTD in hospitalised adults, and by necessity the research will be undertaken on patients accessing secondary healthcare requiring acute medical care. Some patients will be admitted 'out of hours' (i.e. evenings, nights and/or weekends) and may be discharged or die before the research team have time to approach these individuals for consent. Those who are discharged home after a short interval are those most likely to represent mild disease. Individuals who die shortly after admission are likely to be either elderly, frail or have extensive/severe pre-existing medical conditions. These patients are those most likely to represent severe disease with adverse outcomes, and therefore most likely to benefit from any public health intervention or improvement in healthcare resource allocation that may be enabled by the insights provided by this study. However, not all elderly, frail or patients with co-morbid disease have severe disease, and it is therefore not possible to extrapolate or generalise the data obtained from individuals who consent to all patients admitted. To fully understand, describe and account for acute LRTD and its subgroups of disease it is essential to undertake comprehensive surveillance activity inclusive of all individuals requiring hospital-level care following presentation with acute LRTD. An accurate evaluation of disease incidence, including the incidence of pneumonia, LRTI and other disease subgroups or estimation of disease incidence by risk factor (such as age, gender, socioeconomic status), requires the inclusion and accurate data capture of all individuals admitted within the defined geographical area over a defined period.

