5.2.3 Postcode (to sector level)

Sector level postcode is required to estimate the socioeconomic status of individuals affected with respiratory disease, and to undertake geotemporal analysis of acute LRTD allowing for mathematical modelling of infection. Determining which localities and socioeconomic groups are most at risk of disease and adverse outcomes is important in determining the availability and distribution public health care interventions, including but not limited to vaccination programmes. Furthermore, the potential impact of other interventions designed to modify risk factors such as comorbid disease, environmental factors and access or availability of healthcare resources can be appropriately assessed and provided based on the data provided by this study.

Mathematically modelling disease patterns and spread in time and place allows for better understanding of how disease outbreaks and incidence of disease occurs in a population, and will provide a generalisable model that can be used both within this population and extrapolated to other populations. This will also not only provide better understanding of disease but also provision of better health care resources to reduce disease morbidity and mortality.

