9.1 Study size

Expected study size was calculated using both a retrospective coding data from 2018-2019, and a 21-day prospective audit of adult patients admitted to the Acute Medical Unit at NBT. It should be noted that both methods used to calculate estimated patient numbers were conducted in a time period before the COVID-19 pandemic. Both methods calculated an Avon CAP patient cohort approximately 7,000 adult patients per annum at NBT, and assuming all 2 hospital sites have similar patient numbers, the envisaged patient cohort before COVID-19 was 14,000 patients per annum. However, given the COVID-19 pandemic we expect a significantly large sample size, which is likely to approximate 23,000 patients per annum across the 2 sites. Number of adults in surveillance population is approximately 630,000, yielding expected LRTD incidence of >3,600 per 100,000 population annually (3.65 per 100 person years; 95% CI: 3.60 to 3.70).

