9.4.1 Denominator

The two hospitals included in the study serve much of the Bristol population. However, there is likely some cross over at the geographical borders, for example with Bath Hospital. It is expected that this may be directional towards Bristol, as both hospitals are tertiary referral centres so individuals may preferentially attend in Bristol rather than Bath, which is a district general hospital. The team will have assessed the degree of such cross over by the analysis phase so that a correction can be factored into the denominator, but this will be by estimation.

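### Incidence is meant for residents of a defined area, but the events counted have no residence rule, and cross-border inflow is left to an estimated denominator correction although postcode sector is held

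*Protocol*

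**What the plan says.** **Target of the rate.** Section 3.1 makes population-based incidence of hospitalised community-acquired LRTI the primary outcome. Section 1.5 rests this on near-complete capture of admissions among the residents of a delineated region, and section 2.1 names the area's defined population as the denominator.

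**Events counted.** Section 2.2 takes in every adult presenting to the two Trusts with features of acute LRTD. Section 5.1 says that an accurate incidence "requires the inclusion and accurate data capture of all individuals admitted within the defined geographical area over a defined period", and section 1.6 is to the same effect. The criteria in sections 4.4.1 and 4.4.2 contain no residence condition.

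**Planning rate.** Section 9.1 expects a yearly total "which is likely to approximate 23,000 patients per annum across the 2 sites" and continues: "Number of adults in surveillance population is approximately 630,000, yielding expected LRTD incidence of >3,600 per 100,000 population annually". It prints the rate as "3.65 per 100 person years; 95% CI: 3.60 to 3.70".

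**Cross-border flow.** Section 9.4.1 regards some cross-over as likely and says that it may run towards Bristol because both hospitals are tertiary centres. The remedy is to assess the cross-over by the analysis phase "so that a correction can be factored into the denominator, but this will be by estimation".

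**Data that locate the patient.** Section 5.2 lists postcode sector among the items collected without consent, and sections 7.1.1 and 8.1.1 use postcode in the consented and non-consented arms. Its stated purposes in section 5.2.3 are socioeconomic ("Sector level postcode is required to estimate the socioeconomic status of individuals affected with respiratory disease") and geotemporal. Section 11.2 then separates postcode from the pseudonymised clinical dataset. Section 6.2 gives another route: with consent, the patient's GP practice is recorded to build a denominator.

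**The concern.** A population-based rate needs events and person-time from the same people. Here the person-time belongs to a defined area, while the events are defined by where the patient was admitted. An admitted non-resident adds an event but no person-time. A resident admitted elsewhere adds person-time but no event.

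The protocol sees the first problem but commits to the weaker remedy. Adjusting the denominator by an estimate replaces a quantity that could be observed for each patient with one that has to be assumed. The objectives also ask for rates by pathogen and, for RSV, by underlying risk condition (sections 3.2.1, 3.2.3 and 3.2.4). A correction that suits the overall rate suits those rates only if inflow is the same in each group, and the protocol makes no such claim.

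The data split adds a practical risk. Unless residence is named as a purpose and a flag is exported, the routine analysis dataset will not show who lives in the catchment.

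**Working it through.** **Inputs**

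- N = 23,000 expected patients a year and D = 630,000 adults, both from section 9.1.
- f = true share of counted events that are in non-residents; f̂ = the share assumed when the denominator is corrected; g = share of residents' events admitted outside the two Trusts. The documents give none of these. The values below are assumptions to show the range.

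**Step 1: reproduce the printed rate.** 23,000 / 630,000 = 3.651 per 100 person-years. The Poisson 95% interval is (23,000 ± 1.96 × √23,000) / 630,000 = 3.604 to 3.698, which agrees with the printed 3.65 (3.60 to 3.70). The relative half-width is 1.96 / √23,000 = 1.3%.

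**Step 2: inflow with no correction and no outflow.** The resident rate is 3.651 × (1 − f), and the crude rate overstates it by 1/(1 − f) − 1.

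| f | resident rate per 100 | overstatement |
|---|---|---|
| 2% | 3.58 | 2.0% |
| 5% | 3.47 | 5.3% |
| 10% | 3.29 | 11.1% |

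**Step 3: inflow with the planned kind of correction.** Section 9.4.1 gives no formula. On the simplest reading the denominator becomes D / (1 − f̂), so the remaining error is (1 − f̂)/(1 − f) − 1. For f = 5% and f̂ = 2%, the denominator is 642,857 and the rate 3.578 against a true 3.468, an error of +3.2%. For f = 5% and f̂ = 10%, the denominator is 700,000 and the rate 3.286, an error of −5.3%.

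| true f | f̂ = 2% | f̂ = 5% | f̂ = 10% |
|---|---|---|---|
| 2% | 0 | −3.1% | −8.2% |
| 5% | +3.2% | 0 | −5.3% |
| 10% | +8.9% | +5.6% | 0 |

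Every non-zero entry exceeds 1.3%.

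**Step 4: outflow as well, still uncorrected.** The crude error is (1 − g)/(1 − f) − 1. With f = 5% it is +5.3% at g = 0, zero at g = 5% and −5.3% at g = 10%. The direction of the error is not fixed.

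**Step 5: what a residence rule removes.** With only residents counted, the rate is N(1 − f)/D against a true N(1 − f)/[(1 − g)D], a ratio of 1 − g. The inflow share drops out because it is observed. What remains is outflow: −2% at g = 2% and −5% at g = 5%, before any correction for it.

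**The case against.** The strongest reply is that section 9.4.1 discloses the limitation and plans to correct it, that section 9.3 leaves detailed methods to a SAP that is not shown, and that section 1.5 already signals a resident-based rate. On this view the eligibility criteria say who is enrolled, not which events enter a rate, and a catchment list is ordinary SAP content. Part of this stands: the SAP may well restrict the numerator. But the protocol is not silent. It names a method, and by section 9.3 a major change to the primary endpoint definition or its analysis belongs in a protocol amendment.

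Some stronger readings are tempting and are not supported.

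- A reader might infer that the reported rates are certain to be too high. The planned correction offsets inflow, and over-correction would make the rate too low. Residents admitted elsewhere, and patients who decline consent and appear only in the screening log (section 1.6), also pull it down. Section 9.4.1 itself says only that the flow may be towards Bristol.
- A reader might infer that one crude factor will be applied throughout. The text does not say whether the correction will vary by age or other group.
- A reader might infer that ICU share and 30-day mortality are inflated by sicker patients transferred in. The documents do not say that such patients are sicker. Those outcomes are described among hospitalisations, and a numerator rule for incidence would not change them. The transfer wording in section 4.4.2 concerns onset of illness after 48 hours in hospital and would fit a transfer between the two Bristol Trusts equally well.

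Nor is the estimated correction the only route mentioned, since section 6.2 offers GP registration. That route is described for consented patients only, a registered population need not be the resident one, and it is not reconciled with section 9.4.1. Postcode use is also not closed off: section 11.3 allows identifying data to be used for a specific reason. Residence for the incidence numerator is simply not named as one.

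**Conclusion.** The concern holds as a mismatch between the population the rate describes and the events the protocol says it will count, with a stated remedy weaker than the data allow. It concerns the primary outcome. Net inflow would inflate the rate to the extent that the correction falls short, and over-correction would deflate it.

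At an assumed true non-resident share of 5%, the error left is about +3% if 2% is assumed and about −5% if 10% is assumed, against ±1.3% sampling error in the planning rate. These sizes rest on assumed shares, on the simplest form of correction and, in Step 3, on no outflow. They are applied to a planning projection for all LRTD, which section 9.1 raises from 14,000 to 23,000 patients in expectation of COVID-19, and not to the primary LRTI rate. They show that the choice of method can matter more than sampling error. They do not estimate the bias in the study's results.

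**What to change.** In section 9.4.1, and wherever incidence is defined:

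1. Define the catchment as a list of postcode sectors. A sector that straddles a boundary is then either in or out, for events and population alike.
2. Derive an in-catchment flag from the postcode sector before the data are split under section 11.2, and export it as a calculated field. Add residence for incidence to the purposes in section 5.2.3.
3. Count only in-catchment events in incidence numerators, and use the adult population of the same sectors, by age band, as the denominator.
4. Reserve estimation for residents admitted outside the study hospitals, and report the rate with and without that adjustment.
5. State how the GP-registration denominator in section 6.2 relates to this rule, or withdraw it for incidence.
6. Keep non-residents in the descriptive and vaccine-effectiveness analyses.
7. Label the 3.65 in section 9.1 as all expected admissions before residence restriction.

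The cost is one derived field, a short rewrite of section 9.4.1 and matching lines in the SAP. The numerator will be somewhat smaller. Outflow still has to be estimated, and by Step 5 the resident-only rate will be too low until that is done. The plan also needs adult population figures by postcode sector, which the protocol does not mention.

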9.4.2 Representativeness

Hospitalized individuals admitted with LRTD who meet the eligibility criteria will be invited to participate in the enhanced diagnostic testing portion of the study. It is possible there could be bias in the refusals being different from those who do take part, for example those with most severe disease. Further, if recruitment for enhanced diagnostic testing cannot be performed at all times (eg, weekends, overnights, and holidays), some patients with acute LRTD may not be able to participate in the enhanced diagnostic testing portion of the study on that basis. The representativeness of enhanced diagnostic testing participants will be established by comparing the groups that have accepted and declined using eCRF data.

9.4.3 Recruitment completeness

It is possible patients may be missed by virtue of their pathway through the hospital being atypical, the time of admission or a human error factor. This would be a random error so should not bias the study. Every effort will be made to identify such patients through ongoing audits for surveillance completeness (e.g., via radiological records, ICD discharge codes, or microbiology tests ordered). A second factor may be the inability to collect samples from all consented participants, possibly through their refusal or inability to provide them. This will be addressed through appropriate training of staff in the importance of and methods to obtain as comprehensive a set as possible, while respecting patient choice and well-being.

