Pneumonia study inclusion criteria are not the only source of underestimation of pneumococcal burden – under or alternate diagnosis also contributes. Presenting complaints as well as signs and symptoms in older patients with pneumonia are often atypical and may lead to missed or incorrect admission diagnoses (Henig & Kaye, 2017). Also, pneumonia may be a secondary to or an underlying cause of the main presenting complaint, such as in patients with altered level of consciousness, cerebrovascular accidents (CVA), congestive heart failure (CHF), or COPD exacerbations. In these scenarios, pneumonia may not be the primary diagnosis code recorded for the hospitalization or may not be coded as an associated diagnosis at all. On this basis, there is a need to assess the burden of pneumococcal disease in the larger group of patients presenting with acute lower respiratory disease – not just those with a formal pneumonia diagnosis. Acute lower respiratory tract disease (LRTD) in adults includes pneumonia (all types); bronchitis; exacerbations of chronic obstructive pulmonary disease, congestive heart failure, asthma, and other underlying pulmonary disease (e.g., cystic fibrosis); acute respiratory distress syndrome (ARDS); and other acute lower respiratory disease, i.e., any condition involving acute lower respiratory pathology (i.e., effects trachea, bronchi, bronchioles, or lungs in opinion of treating/study physician). Comprehensive assessment of all LRTD is needed to identify the disease burden due lower respiratory tract infection.

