3.1 Primary outcome

To estimate population-based incidence of community-acquired LRTI hospitalizations during and following the COVID-19 pandemic, overall and for community-acquired pneumonia.

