4.2 Active surveillance and screening

The detailed screening methods to conduct active surveillance will be determined by the site and described in full in a Surveillance Manual which will be created and managed by the Investigator and reviewed by Pfizer collaborators. The feasibility studies conducted prior to the surveillance study implementation will inform the detail of surveillance activities and screening processes at both locations.

In essence, any adult inpatients ≥ 18 years old presenting to one of the participating hospitals displaying the specified symptoms of LRTD or with a clinical diagnosis consistent with LRTD will be included in the screening activities, including those with exacerbations of COPD and CHF accompanied

by respiratory symptoms. Screening for potential Avon CAP study participants will be undertaken by a member of the clinical team at each hospital site, usually a nurse, allied health professional (e.g. physiotherapist) or doctor. This should be performed at least once a daily during the working week (Mon-Fri), with the first screening round performed at the start of the day. Screening will involve reviewing the medical admission take list (primarily the 'presenting complaint/details' section) to screen patients for entry to the surveillance part of the study. The medical admission list is a real-time electronic based list (internet or other IT system) which can be searched using various parameters including admission time, enabling accurate checking of patient admissions (especially those occurring overnight and at weekends). The medical admission take list also records details of the presenting complaint and/or presumed diagnosis of each patient admitted to the hospital.

Patients admitted through the medical admission take will be excluded if they have a presenting complaint or diagnosis that is not compatible with the study inclusion/exclusion criteria. For example, patients without lower respiratory pathology such as acute pancreatitis, myocardial infarction (NSTEMI or STEMI), stroke or cellulitis would be excluded from entering the surveillance log.

Following consent, participants with LRTD events meeting the screening definition will undergo enhanced diagnostic tests and have their clinical data pseudonymised and entered into the eCRF. All potential participants will be approached regardless of time of admission if they are present during established recruitment periods.

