Avon CAP will undertake systematic and comprehensive surveillance of all adults hospitalized with acute lower respiratory tract disease within a well-defined geographical area. As the demographic and population of Bristol is well described, ascertaining the true burden of acute respiratory infection and describing disease in the context of COVID-19 will allow this study to calculate accurate estimates of incidence. In order to be able to determine the morbidity and mortality associated with acute lower respiratory tract disease, it is necessary that the data collected cover the entire population, as missing any cases within the study area would result in an inaccurate calculation of disease burden. Furthermore, by capturing and detailing precise clinical data, this study will be able to stratify disease by patient factors such as age, gender and ethnicity, as well as by risk factors, including smoking status and pre-existing co-morbid disease including chronic respiratory and cardiovascular conditions. Through this surveillance mechanism all acute respiratory infection in hospitalized adults will also be described by causative pathogen and radiological diagnosis, in addition to capturing patient outcome. The study has three important features:

1. The data will be comprehensive and complete over a defined time period for a defined population area and therefore not subject to the potentially biased ascertainment which weakens other large studies
2. The demographic of the study area is broad in terms of deprivation, minority groups, urban and rural distribution and is in many ways highly representative of the population of England, permitting results to be of value for nationwide planning.
3. The study has substantial confirmed funding which will underpin its viability and successful conduct and is fully embedded within the clinical services of the contributing hospitals, while the anonymised data handling and analysis will be undertaken within the University domain thus not competing for scarce research resources at a time of critical need within the NIHR and NHS research infrastructures.

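### Section 9.4.3 calls missed patients a random error that causes no bias, but any case still missed after audit lowers the incidence in proportion, random or not

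*Protocol*

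**What the plan says.** The primary outcome (Section 3.1) is a population rate: "To estimate population-based incidence of community-acquired LRTI hospitalizations during and following the COVID-19 pandemic", overall and for community-acquired pneumonia.

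Section 9.4.3 lists three ways a patient may escape the surveillance: an atypical pathway through the hospital, the time of admission, and human error. It then states: "This would be a random error so should not bias the study". The next sentence promises continuing completeness audits against radiology records, discharge codes and microbiology requests. Section 6.1 also plans an audit of microbiological testing.

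Section 5, which justifies collecting data without consent, takes the opposite view: "missing any cases within the study area would result in an inaccurate calculation of disease burden".

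Under Section 4.2, screening works from the medical take list, mainly from the presenting-complaint field. Patients described as having no lower respiratory pathology are left out; among the examples, "myocardial infarction (NSTEMI or STEMI), stroke or cellulitis would be excluded from entering the surveillance log". Section 1.3 warns that signs in older patients are often atypical and that "pneumonia may be a secondary to or an underlying cause of the main presenting complaint, such as in patients with altered level of consciousness"; it goes on to name stroke, heart failure and COPD exacerbations.

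The one numerical correction the protocol states is to the denominator, for cross-over at the catchment border (Section 9.4.1).

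**The concern.** Random loss can leave a mean or a proportion among the observed patients unbiased. It cannot leave a count unbiased. When the numerator is the number of cases found and the denominator is a fixed population, a missed case is subtracted and nothing offsets it. The statement in Section 9.4.3 therefore claims a property that the design does not have, and it does so for the primary outcome.

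The listed causes are also not obviously random. Pathway and time of admission are features of the patient and the service. A first sift on presenting complaint is least reliable where the complaint hides the chest disease, which Section 1.3 says happens in older patients. Uneven loss would distort age-specific rates as well as the overall rate.

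The study was set up because earlier studies under-counted. If the protocol treats the remaining under-count as harmless, nothing in it prompts the team to measure that under-count or show its effect.

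**Working it through.** **Inputs from Section 9.1**
- Expected cases per year, D: "which is likely to approximate 23,000 patients per annum across the 2 sites", so 23,000.
- Population, N: "Number of adults in surveillance population is approximately 630,000, yielding expected LRTD incidence of >3,600 per 100,000 population annually", so 630,000.
- Stated rate and interval: "3.65 per 100 person years; 95% CI: 3.60 to 3.70".

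**Assumed input**
- m, the share of eligible cases still missed after audit. The protocol gives no value, so a range is shown.

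**Step 1: reproduce the stated figure**
- Rate = D / N = 23,000 / 630,000 = 3.651 per 100 person-years.
- Poisson 95% CI = (D ± 1.96 × √D) / N. With √23,000 = 151.7, the half-width is about 297 cases, which gives 3.604 to 3.698.
- This agrees with the stated 3.65 (3.60 to 3.70).

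**Step 2: effect of missed cases**

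Expected observed rate = true rate × (1 − m). Only m enters the formula; whether the loss is random does not. Taking 3.651 as the true rate:

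| m (assumed) | Cases lost | Observed rate per 100 person-years | Shift ÷ CI half-width |
|---|---|---|---|
| 1% | 230 | 3.61 | 0.8 |
| 2% | 460 | 3.58 | 1.5 |
| 5% | 1,150 | 3.47 | 3.9 |
| 10% | 2,300 | 3.29 | 7.7 |

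**Step 3: miss that equals the half-width**
- 297 / 23,000 = 1.29%. A residual miss of about 1.3% moves the expected estimate by the whole half-width.

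**Step 4: uneven loss (illustration only)**
- If 15% were missed in older and 5% in younger patients, an old-to-young rate ratio would be multiplied by 0.85 / 0.95 = 0.89.

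These figures are for LRTD, the quantity sized in Section 9.1. The primary outcome is LRTI and pneumonia. The same proportional effect applies there, but the half-width would be wider relative to the rate because the counts are smaller.

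**Step 5: the two statements side by side**
- Section 5 says missing cases makes the burden calculation inaccurate. Section 9.4.3 says it does not bias the study. Step 2 agrees with Section 5.

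**The case against.** The strongest defence is that the sentence sits in a limitations paragraph. It fixes no estimator or eligibility rule, and audits follow it immediately. Detailed analysis belongs to the SAP (Section 9.3), and a completeness adjustment may well be there. This is a fair reason to keep the severity moderate. It does not rescue the sentence, because audits reduce m but do not make the remaining misses harmless.

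A reader might infer several stronger things that the protocol does not support:
- **That missed patients are simply left uncorrected.** The audits in Sections 6.1 and 9.4.3 are meant to recover them. What is not stated is any estimate of, or adjustment for, those still missed.
- **That the screening rule drops stroke or infarction patients who have pneumonia.** The Section 4.2 exclusion is worded for patients without lower respiratory pathology, and the same section screens in COPD and heart failure exacerbations with respiratory symptoms. A masked case could still be lost at list review, but that is a residual risk and not a rule.
- **That night and weekend admissions are lost.** The take list can be searched back by admission time, and patients who leave or die before approach enter the non-consented arm (Sections 1.6 and 10.7).
- **That incidence will be published with Poisson error only.** The interval in Section 9.1 is a study-size expectation and not the analysis plan. It serves here only as a yardstick. Because 23,000 events give a narrow interval, even a small bias looks large against it.
- **That the final estimate is biased downward on net.** Section 9.4.1 expects inflow towards Bristol, which would raise the rate unless fully corrected.

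**Conclusion.** The no-bias statement in Section 9.4.3 is wrong for an incidence and contradicts Section 5. For this source of error the direction is certain: each 1% of cases still missed lowers the rate by 1%. The size is unknown because the residual miss is not given. Under assumed values of 1% to 5%, the expected 3.65 per 100 person-years becomes 3.61 to 3.47, and about 1.3% is enough to equal the stated CI half-width. Greater loss in older patients with atypical presentations is plausible from Sections 1.3 and 4.2 but is not shown. The net error in the final rate also depends on how well catchment inflow is corrected. This should be fixed, but it does not invalidate the design.

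**What to change.** In Section 9.4.3, delete the sentence on random error and state that missed cases bias incidence downward, possibly unevenly across patient groups. Then:
- have the planned audits also cover admissions dropped at take-list review on presenting complaint;
- add eligible patients found by audit to the numerator;
- report audit-based completeness by site, age group and admission time;
- present incidence raw, and alongside it a completeness-adjusted estimate or a sensitivity range over plausible residual misses.

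Two-source capture-recapture is an option but not required. Chest imaging, respiratory microbiology and respiratory coding are all more likely once a respiratory illness has been recognised, so the sources are probably positively dependent. That would overstate completeness and under-correct the rate.

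The cost is a wording change, a wider audit sample and some extra analysis, mostly on audits already planned. The downside is that the adjusted figure rests on assumptions, which is why the raw figure should stand beside it.
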